5.7.3.5. Pregnancy testing

The results of the pregnancy test (positive, negative, borderline, invalid) will be summarized at each scheduled time point as frequency distributions.

5.7.3.6. Columbia–Suicide Severity Rating Scale

The Columbia–Suicide Severity Rating Scale (C-SSRS) is an assessment tool that evaluates suicidal ideation and behavior. The following outcomes are C-SSRS categories and have binary responses (yes/no). The categories have been re-ordered from the actual scale to facilitate the definitions of the composite and comparative endpoints, and to enable clarity in the presentation of the results:

Suicidal Ideation	Category 1	Wish to be dead	
	Category 2	Non-specific active suicidal thoughts	
	Category 3 Active suicidal ideation with any methods (not plan intent to act		
	Category 4	Active suicidal ideation with some intent to act, without specific plan	
	Category 5	Active suicidal ideation with specific plan and intent	
Suicidal behavior	Category 6	Preparatory acts or behavior	
	Category 7	Aborted attempt	
	Category 8	Interrupted attempt	
	Category 9	Actual attempt (non-fatal)	
	Category 10	Completed suicide	

Non-suicidal self-injurious behavior is also a C-SSRS outcome (although not suicide-related) and has a binary response (yes/no).

Composite endpoints based on the above categories are defined below:

- *Suicidal ideation*: A "yes" answer at any time during treatment to any one of the five suicidal ideation questions (Categories 1-5) on the C-SSRS.
- *Suicidal behavior*: A "yes" answer at any time during treatment to any one of the five suicidal behavior questions (Categories 6-10) on the C-SSRS.

• *Suicidal ideation or behavior*: A "yes" answer at any time during treatment to any one of the ten suicidal ideation and behavior questions (Categories 1-10) on the C-SSRS.

The following outcome is a numerical score derived from the C-SSRS categories. The score is created at each assessment for each patient.

Suicidal ideation score: The maximum suicidal ideation category (1-5 on the C-SSRS) present at the assessment. Assign a score of 0 if no ideation is present.

Note that missing data should not be imputed.

The incidence of the 11 items (the 10 categories and the 'Non-suicidal self-injurious behavior') and the 3 composite endpoints will be summarized as frequency distributions at screening and/or baseline (combined), and at any of the assessments during treatment (worst score during treatment).

The maximum score (from the 10 categories) assigned for each subject will also be summarized into one of three broad categories: No suicidal ideation or behavior (0), Suicidal ideation (1 - 5), Suicidal behavior (6 - 10). Shifts from the screening/baseline value to the maximum category during treatment will be summarized as frequency distributions.

For the suicidal ideation score the shift from screening/baseline to the maximum during treatment will be summarized as frequency distributions.

5.7.3.7. Other Safety Parameters

Not applicable

5.8. Other Analyses

5.8.1. Pharmacokinetics

Not applicable

5.8.2. Immunogenicity

Not applicable

5.8.3. Pharmacodynamics

Not applicable

5.8.4. Pharmacokinetic/Pharmacodynamic Relationships

Not applicable

5.8.5. Biomarkers

Details of the analysis plan and summary of results from both biomarker and pharmacogenomic analyses will be reported separately.

5.8.6. Health Economics

Not applicable

5.8.7. Definition of Subgroups

The following subgroups will be used to summarize parameters:

Subgroup	Variant	Definition
Sex	1	• Male
		• Female
Age Group	1	• Adult [18-64]
		• Elderly [>=65]
Number of previous	1	• 2
treatment failures		• >=3
Class of continued oral AD	1	SNRI
		• SSRI

The following parameters will be analyzed as described in the respective sections for the subgroups:

- Selected demographic and disease characteristics;
- The primary parameter and the major secondary parameter;
- MADRS;
- CGI-S and CGI-C;
- PHQ-9;
- QLDS;
- Selected AE parameters (including AEs of special interest).

5.9. Interim Analyses

Not applicable.

5.10. Follow-up Phase

The follow-up phase starts when a randomized participant discontinues study intervention. The starting visit of the follow-up phase is the visit when the treatment discontinuation occurs, or the visit closest to the treatment discontinuation. The follow-up analysis set will be used for all analyses. Analyses will be presenting observed data only and uses descriptive methods. For continuous parameters the change from starting visit of the follow-up phase will also be summarized. Data will be presented by group where to participant was randomized to and overall.

The following parameters will be analyzed as described in the respective sections:

- Selected demographic and disease characteristics;
- Treatment administered;
- Remission and relapse;
- MADRS;
- CGI-S;

- PHQ-9;
- QLDS;
- (Serious) Adverse events recorded during a Janssen treatment for depression.

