		(0	dd w	eek v	isits a	are C	ONLY	l for	parti	cipar	nts in	the e	esket	amin	e arn	a witl	h one	ce we	ekly	dosin	ıg fre	quen	cy)		Every			2 weeks
																									2	4	1	after last
Week	9	10	11	12	13	14	15	16	17	18	19	20	21	22	23	24	25	26	27	28	29	30	31	32	weeks	weeks		dose
Visit Window (Days)	±3	±3	±3	±3	±3	±3	±3	±3	±3	±3	±3	±3	±3	±3	±3	±3	±3	±3	±3	±3	±3	±3	±3	±3	±3	±3		±2
Vital signs ^{j,k} / nasal examination ^{k,l} (esketamine arm)																								x			х	x
Additional safety assessments (esketamine arm)																												
Vital signs predose	Х	X	X	X	X	X	X	X	Х	X	Х	Х	Х	Х	Х	Х	Х	X	X	X	X	Х	X					
Vital signs postdose ^{j,m}	Х	Х	Х	Х	Х	Х	Х	Х	Х	Х	Х	Х	Х	Х	Х	Х	Х	Х	Х	Х	Х	Х	Х					
Nasal examination predose ^l	х	x	x	x	x	x	x	x	x	x	x	x	х	x	x	x	х	x	x	x	x	x	x					
Study intervention procedures																												
Dispense QTP XR (comparator arm) ⁿ		Xº		Xº		Xº		Xº		Xº		X°		Xº		Xº		Xº		Xº		Xº						
Nasal treatment sessions ^{p,q} (esketamine arm)	Xr	Xr	Xr	Xr	Xr	Xr	Xr	Xr	Xr	Xr	Xr	Xr	Xr	Xr	Xr	Xr	Xr	Xr	Xr	Xr	Xr	Xr	x					
Drug accountability: esketamine/QTP XR				x				x				x				x				x				х			х	
Medication compliance counseling	х	х	х	х	x	x	х	x	х	х	х	х	х	х	х	х	х	х	х	х	х	х	х	х			х	
Biomarker evaluations	(opti	onal))						_		_		_				-					_		_				
Blood sample ^s																											Xt	
Menstrual cycle information																											X ^t	
Ongoing																												
Concomitant therapy/ psychotherapy		х		х		х		х		х		х		x		x		х		х		х		х	х	х	х	х
Adverse events		Х		Х		Х		Х		Х		Х		Х		Х		Х		Х		Х		Х	Xu	Xu	Х	Х

NOTES: If the SSRI/SNRI is discontinued at any time during the maintenance phase, the esketamine nasal spray or quetiapine XR must also be discontinued. The participant will be switched to an alternative standard of care treatment at the discretion of the investigator and continue follow-up visits through Week 32.

If esketamine nasal spray or quetiapine XR is discontinued at any time during the maintenance phase, the participant will be switched to an alternative standard of care treatment, which may or may not include the continuing SSRI/SNRI, at the discretion of the investigator and continue follow-up visits through Week 32. If determined by the investigator that the alternative standard of care will include esketamine nasal spray (when commercially available in country of participation) or QTP XR, it will not be provided to the participant, rather, the investigator must prescribe the medication to the participant.

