- Participant must have been treated with at least 2 different antidepressive substance classes among the treatments taken at an adequate dosage for an adequate duration of at least 6 weeks resulting in nonresponse in the current moderate to severe depressive episode (including the current treatment with an SSRI/SNRI).
- Participant must be on a single oral SSRI/SNRI on Day 1 prior to randomization.
 - Participants who are taking combination ADs and/or augmentation (other than quetiapine XR which is exclusionary at doses >50 mg/day) for the current moderate to severe depressive episode at screening are eligible for the study. All AD treatments, including any augmenting substances, must be stopped prior to randomization on Day 1 according to applicable SmPCs (or local equivalents, if applicable), except the SSRI/SNRI to be continued.

The study has 4 phases: an up-to-14-day screening phase, an 8-week acute phase, a 24-week maintenance phase, and a 2-week safety follow-up phase. During the acute phase, participants in the esketamine arm will have twice-weekly visits from Week 1 to Week 4 and once weekly visits from Week 5 to Week 8; during the maintenance phase from Week 9 to Week 32, visits will be once weekly or every 2 weeks (even weeks) based on dosing. Participants in the comparator arm will have weekly visits from Week 1 to Week 4, and then every 2 weeks for the remainder of the acute phase (Week 6 and Week 8) and the maintenance phase (Week 10, Week 12, etc) through Week 32. All participants have a safety follow-up visit 2 weeks following the last dose of study intervention. The total duration of the study is approximately 36 weeks for all participants.

A total of 622 participants will be randomly assigned on Day 1 (baseline) in a 1:1 ratio to 1 of 2 open-label study intervention arms (311 participants per arm):

- **Esketamine Arm:** Participants will continue to take their current SSRI/SNRI in combination with esketamine nasal spray.
 - Study intervention (ie, esketamine nasal spray in combination with a continuing SSRI/SNRI) will be administered as described in Section 6.1.1.
- **Comparator Arm:** Participants will continue to take their current SSRI/SNRI which will be augmented with quetiapine XR as per its SmPC (or local equivalent, if applicable).
 - Study intervention (ie, quetiapine XR in combination with a continuing SSRI/SNRI) will be administered as described in Section 6.1.2.

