The frequency of nasal treatment sessions for participants in the esketamine arm can be further individualized during this phase on even week visits (Week 10, Week 12, etc) from once weekly to every 2 weeks based on the severity of depressive symptoms and at the discretion of the investigator. If participants show early signs of worsening of depressive symptoms after reduced frequency of the nasal treatment sessions, the frequency can be changed back to once weekly at any visit. Nasal treatment session frequency should be increased prior to increasing the esketamine nasal spray dose during this phase. Uneven week visits will only be performed for participants who are on a once weekly dosing schedule. Recommendations for dose adjustments of esketamine nasal spray based on efficacy and tolerability during the acute and maintenance phases are provided in Section 6.6.1 in Figure 1 and Figure 2, respectively for adults and Figure 3 and Figure 4, respectively for elderly participants and adults of Japanese ancestry.

During this phase, the treatment continuation assessment of study intervention (Week 12, Week 16, etc) (see Section 4.1, Table 1) should be the basis for the decision to continue study intervention.

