1.2. Study Design

Study design and patient selection

This is a randomized, open-label, rater-blinded, active-controlled, international, multicenter study in participants 18 to 74 years of age, inclusive, with treatment-resistant MDD.

To be eligible for enrollment in the study:

- Participant must be on a *current* antidepressive treatment that includes an SSRI/SNRI at screening that resulted in nonresponse (less than 25% improvement of symptoms) after having been given at an adequate dosage (been uptitrated to maximum tolerated dose; based on antidepressive dosages from Summary of Product Characteristics [SmPC; or local equivalent, if applicable]) for an adequate duration of at least 6 weeks; however, at screening the participant must show signs of minimal clinical improvement to be eligible for the study.
- In addition to the current antidepressive treatment, participant must have documented nonresponse within the current moderate to severe depressive episode to at least 1 but not more than 5 different, previous consecutive treatments with ADs taken at an adequate dosage for an adequate duration of at least 6 weeks and that each prior AD treatment did not produce any significant improvement (less than 25% improvement of symptoms).
- Participant must have been treated with at least 2 different antidepressive substance classes among the failed treatments in the current moderate to severe depressive episode (including the current treatment with an SSRI/SNRI).
- Participant must be on a single oral SSRI/SNRI on Day 1 prior to randomization.

Study phases

The study has 4 phases: an up-to-14-day screening phase, an 8-week acute phase, a 24-week maintenance phase, and a 2-week safety follow-up phase. During the acute phase, participants in the esketamine arm will have twice-weekly visits from Week 1 to Week 4 and once-weekly visits from Week 5 to Week 8; during the maintenance phase from Week 9 to Week 32, visits will be once weekly or every 2 weeks (even weeks) based on dosing. Participants in the comparator arm will have weekly visits from Week 1 to Week 4, and then every 2 weeks for the remainder of the acute phase (Week 6 and Week 8) and the maintenance phase (Week 10, Week 12, etc) through Week 32. All participants have a safety follow-up visit 2 weeks following the last dose of study

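### SAP 5.10 measures follow-up-phase change from the visit at or nearest discontinuation, where the scale is often unrated (many esketamine visits, most QLDS visits in both arms) and which may fall after the switch

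*SAP*

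**What the plan says.** SAP 5.10 begins the follow-up phase when a randomized participant discontinues study intervention and fixes the reference point: "The starting visit of the follow-up phase is the visit when the treatment discontinuation occurs, or the visit closest to the treatment discontinuation". It then adds: "For continuous parameters the change from starting visit of the follow-up phase will also be summarized". The scales concerned are MADRS, CGI-S, PHQ-9 and QLDS, presented by randomized group and overall. On missing data it says: "Analyses will be presenting observed data only and uses descriptive methods". It gives no fallback for a starting visit at which the scale was not rated.

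Visit frequency differs by arm. Protocol 4.1 states that "participants in the esketamine arm will have twice-weekly visits from Week 1 to Week 4", and then weekly to Week 8. For the other arm it states: "Participants in the comparator arm will have weekly visits from Week 1 to Week 4, and then every 2 weeks". In maintenance, the SAP (1.2) says that esketamine "visits will be once weekly or every 2 weeks (even weeks) based on dosing", and Protocol 6.1.1.4 adds: "Uneven week visits will only be performed for participants who are on a once weekly dosing schedule".

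The Schedule of Activities (Protocol 1.3.1 and 1.3.2) rates each scale on a subset of these visits, with the same rating days in both arms. For the visit at which a switch is made before Week 8, a footnote to 1.3.1 adds only the optional biomarker sample and menstrual cycle information. The early study withdrawal visit does carry all four scales, but it applies to leaving the study, not to stopping treatment and staying in follow-up.

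**The concern.** A change score needs a start value. If the starting visit carries no rating of the scale, an observed-data analysis drops that participant from the change summary. Take a participant on weekly esketamine who stops at the Week 13 visit. None of the four scales is scheduled there, so all four changes are missing, although MADRS and PHQ-9 were due one week earlier.

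A second weakness concerns stops between visits. Closeness runs in both directions, so the starting visit can lie after the stop. The reference value then already includes some time on the alternative treatment, and part of the change that the summary is meant to show is absorbed into it.

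At stake is how far the two arms' follow-up-phase change summaries can be compared. The extra dosing-only visits exist only in the esketamine arm, so the rule loses start values unequally by arm. The loss may also be selective. Stops for lack of benefit will tend to occur at decision visits where the scales are rated, whereas stops for tolerability can occur at dosing-only visits where they are not.

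**Working it through.** The plan states no figure for this analysis, so there is none to reproduce. The check counts scheduled post-baseline visits with no rating of each scale.

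**Visits** (Protocol 1.3.1, 1.3.2, 4.1, 6.1.1.4)
- Esketamine, acute: Days 4, 8, 11, 15, 18, 22, 25, 29, 36, 43, 50, 57 = 12.
- Comparator, acute: Days 8, 15, 22, 29, 43, 57 = 6.
- Maintenance: 24 visits on weekly esketamine (Weeks 9 to 32); 12 on every-2-week esketamine and in the comparator arm (even weeks).

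**Ratings** (both arms)

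| Scale | Acute days after Day 1 | Maintenance weeks |
|---|---|---|
| MADRS | 8, 15, 29, 43, 57 | every even week (12) |
| PHQ-9 | 15, 29, 43, 57 | every even week (12) |
| CGI-S | 8, 15, 22, 29, 57 | 12, 16, 20, 24, 28, 32 (6) |
| QLDS | 29, 57 | 12, 16, 20, 24, 28, 32 (6) |

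The esketamine-only visits (Days 4, 11, 18, 25, 36, 50 and the odd maintenance weeks) carry none of the four scales.

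**Unrated share** = (acute unrated + maintenance unrated) / (acute visits + maintenance visits)

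| Scale | Esketamine weekly | Esketamine every 2 weeks | Comparator |
|---|---|---|---|
| MADRS | (7+12)/(12+24) = 19/36 = 53% | (7+0)/(12+12) = 7/24 = 29% | (1+0)/(6+12) = 1/18 = 6% |
| PHQ-9 | (8+12)/36 = 20/36 = 56% | (8+0)/24 = 8/24 = 33% | (2+0)/18 = 2/18 = 11% |
| CGI-S | (7+18)/36 = 25/36 = 69% | (7+6)/24 = 13/24 = 54% | (1+6)/18 = 7/18 = 39% |
| QLDS | (10+18)/36 = 28/36 = 78% | (10+6)/24 = 16/24 = 67% | (4+6)/18 = 10/18 = 56% |

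Esketamine dosing frequency may change during maintenance, so an individual can fall between the first two columns.

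**Reweighting by phase.** Protocol 9.2 assumes 17.5% discontinuation by Week 8 in both arms, then 10% (esketamine) and 20% (comparator) to Week 32. The later rates are stated for Week 8 remitters; applying them to everyone still on treatment is an assumption. The phase weights are 0.175 and 0.825 × 0.10 = 0.0825 (esketamine) or 0.825 × 0.20 = 0.165 (comparator). For MADRS:
- Weekly esketamine: (0.175 × 7/12 + 0.0825 × 12/24) / 0.2575 = 56%.
- Every-2-week esketamine: (0.175 × 7/12 + 0) / 0.2575 = 40%.
- Comparator: (0.175 × 1/6 + 0) / 0.34 = 9%.

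For QLDS the same calculation gives 73% to 81% on esketamine and 59% on comparator. The direction is unchanged.

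**Stops between visits.** With Week w at Day 7w + 1, Week 12 is Day 85, Week 13 is Day 92 and Week 14 is Day 99. Consider a stop on Day 95, matched to the fixed calendar. For a comparator or every-2-week participant, the candidates are 10 days before and 4 days after, so Day 99 is chosen, after the stop. For a weekly esketamine participant, Day 92 is closest (3 days before against 4 after); it precedes the stop but carries no rating.

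With stopping uniform over Days 2 to 224 and ties going to the later visit, the closest visit falls after the stop in 43% (weekly esketamine), 48% (every 2 weeks) and 49% (comparator) on the fixed calendar. If instead the next visit is 14 days after the stop, the figure is 0% in every group.

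**The case against.** Several points on the other side stand.

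- **Visits are not participants.** Stopping is not spread evenly. The Week 4 benefit assessment and the continuation assessments at Week 8 and every 4 weeks after fall on visits where all four scales are rated. The quetiapine tolerability check at the end of Week 2 falls on Day 15, where MADRS, PHQ-9 and CGI-S are rated, though QLDS is not. A reader might take the shares above as the proportion of participants who lose a change score; the documents do not support that.
- **Most visits are not unrated in every group.** For the comparator, only 6%, 11% and 39% of visits lack MADRS, PHQ-9 and CGI-S. On every-2-week esketamine, MADRS and PHQ-9 are unrated at 29% and 33%. Only QLDS is unrated at most visits in both arms.
- **Post-switch references are not an esketamine problem.** A reader might infer that they are more frequent there. On the fixed calendar they are slightly less frequent. Protocol 8.3.1 places the safety follow-up visit 2 weeks after the last dose, which makes the preceding visit the usual choice. Ratings on a dosing day also precede the dose (Protocol 8.1.1), so a rating at the visit where esketamine is stopped is not post-switch.
- **Other post-stop information is planned.** Protocol 9.4.2 has a sensitivity analysis on observed status after stopping, Protocol 9.4.4 tabulates later adverse events, and SAP 5.10 itself summarises remission, relapse and observed scores without needing a start value.

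One further defence only partly holds. SAP 5.1.1 cites parameter-specific visit windows in a spreadsheet that is not part of the documents, so closest visit could mean the closest visit with that scale. The change would then not be missing, but for a 4-weekly scale on the fixed calendar the reference could lie up to about 2 weeks either side of the stop. SAP 5.10 does not refer to those windows, and two programmers could each follow its text and obtain different populations and different references.

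**Conclusion.** The point holds as a defect in the reference rule. Followed literally, SAP 5.10 gives no start value at many esketamine visits and at most QLDS visits in both arms, and the unrated share is higher on esketamine for all four scales. It also permits a reference taken after the switch in either arm, with a frequency that depends on how visits are scheduled after the stop: 43% to 49% on a fixed calendar, none if the next visit is 14 days later.

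The sizes rest on the scheduled visits, on reading the starting visit as a single visit shared by all scales, and, for the between-visit figures, on uniform stopping days. They do not estimate how many participants are affected. The analysis is descriptive, within the follow-up analysis set, and leaves the primary and key secondary tests untouched. This is a minor improvement worth making because it is cheap.

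**What to change.** In SAP 5.10, define the follow-up reference separately for each scale as the last non-missing value on or before the date study intervention was discontinued. Summarise change from that value and report its age in days at discontinuation. Flag, or show separately, participants whose only such value is Day 1.

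The cost is SAP wording and a little programming; no new data are needed. There are two downsides. Some references will be up to about 4 weeks old, given the 28-day spacing of QLDS and, from Week 4, of CGI-S. For very early stops the reference is the study baseline: before Day 8 for MADRS and CGI-S, before Day 15 for PHQ-9 and before Day 29 for QLDS. In those cases the summary becomes change from baseline, which is why they should be shown separately.

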Adverse Event Reporting Following Early Discontinuation of Study Intervention

For participants who discontinue study intervention early, the safety follow-up visit will be performed 2 weeks after their last dose of study intervention. These participants will remain in the study and continue to return for follow-up visits every 2 weeks through Week 32.

For participants who discontinue study intervention early but agree to continue the bi-weekly follow-up assessments until Week 32 of the study:

- 1. If their alternative standard of care treatment includes commercial esketamine or another Janssen medicinal product for depression, AEs will continue to be collected after completion of the safety follow-up visit until Week 32 of the study.
- 2. If their alternative standard of care treatment does not include commercial esketamine or another Janssen medication for depression, AEs will not be systemically collected after completion of the safety follow-up visit. For AEs that are not systematically collected (including AEs for Janssen medicinal products not indicated for depression) and where the participating physician considers there is at least a reasonable possibility of a causal relationship to a medicinal product (ie, spontaneous adverse drug reactions), the participating physician is requested to notify the manufacturer (ie, Janssen or other manufacturer) of the medicinal product or the appropriate regulatory/competent authority through the national spontaneous reporting system as soon as possible.

As described above, all SAEs spontaneously reported within 30 days after the last dose of study intervention must be reported using the Serious Adverse Event Form.)

Where available, reports of spontaneous adverse drug reactions will be summarized in the clinical study report.

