4. POPULATIONS (ANALYSIS SETS) FOR ANALYSIS

The following analysis sets will be used in this SAP:

Analysis Sets	Description	
Enrolled Analysis Set	All participants who sign the ICF	
Full Analysis Set (FAS)	The full analysis set includes all randomized	
	participants.	

Analysis Sets	Description	
Safety Analysis Set	The safety analysis set includes all randomized participants who received at least 1 dose of any study	
	intervention.	
Follow-up Analysis Set	The follow-up analysis set includes all randomized	
	participants who received at least 1 dose of any study	
	intervention, and who discontinue study intervention.	

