5.6. Tertiary/Exploratory Endpoint(s) Analysis

Not applicable.

5.7. (Other) Safety Analyses

All safety analyses will be based on the safety analysis set (based on actual intervention received), unless otherwise specified.

For all continuous safety variables, descriptive statistics by intervention group will include the N, mean, standard deviation, median, minimum, and maximum. Categorical variables will be summarized by intervention group using frequency counts and percentages.

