5.7.2. Adverse Events

The verbatim terms used in the CRF by investigators to identify adverse events will be coded using the Medical Dictionary for Regulatory Activities (MedDRA). All AEs and special reporting situations, whether serious or non-serious, will be reported from the time a signed and dated ICF is obtained until completion of the participant's 2-week safety follow-up visit. Serious AEs, including those spontaneously reported to the investigator within 30 days after the last dose of study intervention, must be reported.

Any AE occurring at or after the initial administration of study intervention through completion of the participant's 2-week safety follow-up visit is considered to be treatment emergent. Serious AEs reported within 30 days after the last dose of study intervention are also regarded as treatment emergent. If the event occurs on the day of the initial administration of study intervention, and either event time or time of administration are missing, then the event will be assumed to be treatment emergent. If the event date is recorded as partial or completely missing, then the event will be considered to be treatment emergent unless it is known to be prior to the first administration of study intervention based on partial onset date or resolution date. All reported treatmentemergent adverse events will be included in the analysis. For each adverse event, the number and percentage of participants who experience at least 1 occurrence of the given event will be summarized by intervention group.

Summary tables, for the first 8 weeks and for the whole study, will be provided for treatmentemergent adverse events:

- AEs
- Serious AEs (SAEs)
- AEs leading to discontinuation of each study agent within a study intervention
- AEs by severity

- AEs by relationship to each study agent within a study intervention
- AEs leading to dose interruption/dose modification of each study agent within a study intervention.

In addition to the summary tables, listings will be provided for participants who:

- Had SAEs
- Had AEs leading to discontinuation of study intervention.

Incidence of treatment-emergent adverse events of special interest will be summarized, grouped in the following MedDRA-based categories: sedation, dissociation, suicidality, suggestive of abuse potential, cystitis, and hepatic impairment. See Appendix 8 for a list of adverse events in each category.

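### The follow-up-phase adverse event summary in SAP 5.10 counts only events on a Janssen depression product but has all discontinuers as its denominator and randomised arms as its columns, so its percentages should not be read as incidence or its columns as treatment received

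*SAP*

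**What the plan says.** SAP 5.10 starts the follow-up phase when a randomised participant stops study intervention. It makes no exception on the analysis set: "The follow-up analysis set will be used for all analyses". SAP Section 4 defines that set as everyone randomised and given one or more doses of study "intervention, and who discontinue study intervention"; what they take afterwards plays no part.

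On columns, SAP 5.10 states: "Data will be presented by group where to participant was randomized to and overall". This replaces the default in SAP 5.7: "All safety analyses will be based on the safety analysis set (based on actual intervention received), unless otherwise specified".

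The last parameter in the SAP 5.10 list is "Serious) Adverse events recorded during a Janssen treatment for depression". Parameters are to be analysed as in their own sections. For adverse events that is SAP 5.7.2, which gives "the number and percentage of participants who experience at least 1 occurrence of the given event".

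Collection is set by Protocol 8.3.1. If the alternative treatment includes commercial esketamine or another Janssen depression product, "AEs will continue to be collected after completion of the safety follow-up visit until Week 32 of the study". If it does not, "AEs will not be systemically collected after completion of the safety follow-up visit". Protocol 6.1.2 allows a quetiapine-arm participant who stops to be prescribed commercial esketamine where it is available in the country.

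**The concern.** The row's numerator and denominator cover different people. Only participants on a Janssen depression product can contribute an event, yet the denominator holds everyone who discontinued. Someone on other standard of care counts as event-free, although after the safety follow-up visit nobody was systematically collecting their events. In that part of the table, absence of collection looks the same as absence of events.

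The columns add a second difficulty. By the row's own definition, each event under quetiapine arose while the participant was on a Janssen product. Randomised grouping suits the other follow-up parameters, such as MADRS or relapse, where everyone is followed alike. It fits poorly where inclusion depends on a treatment chosen after randomisation. At stake is how a reader interprets the only planned summary of adverse events on a Janssen product after discontinuation.

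**Working it through.** The plan states no follow-up-phase incidence, denominator count or switching share, so there is no figure on this point to reproduce. The check combines the text with one identity.

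**Step 1: the rule as written.**
- Numerator: participants with an event while on a Janssen depression product (SAP 5.10).
- Denominator: all dosed discontinuers (SAP 5.10 with Section 4).
- Statistic: number and percentage of participants (SAP 5.7.2).
- Columns: randomised arm and overall (SAP 5.10).

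Neither document gives this row a separate denominator, an exposure-time denominator or a treatment-received column.

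**Step 2: dilution.** Let f be the share of the follow-up set that takes a Janssen depression product and p the true incidence among those participants. Then

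shown percentage = f × p.

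The documents give neither f nor p, so both are assumed. For p = 50%:

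| f | shown |
|---|---|
| 10% | 0.10 × 50% = 5% |
| 20% | 0.20 × 50% = 10% |
| 40% | 0.40 × 50% = 20% |

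The shown and true values agree only if f = 100%.

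**Step 3: contrast between columns.** Assume the same p = 30% in both arms, with f = 10% in one and 30% in the other. The table shows 0.10 × 30% = 3% against 0.30 × 30% = 9%. That gap comes entirely from switching.

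**Step 4: likely scale of the set.** The planning inputs in Protocol 9.2 and SAP Section 3 reproduce:
- Primary: 0.825 × 50% = 41.25% and 0.825 × 35% = 28.88%, giving 311 per arm at 90% power.
- Key secondary: 41.25% × 0.70 × 0.90 = 25.99% and 28.88% × 0.70 × 0.80 = 16.17%, giving 270 per arm at 80% power.

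Using those inputs:
- Stopped by Week 8: 311 × 0.175 = 54.4 per arm, leaving 256.6.
- Stopped later, esketamine: 256.6 × 0.10 = 25.7, total 80.1.
- Stopped later, quetiapine: 256.6 × 0.20 = 51.3, total 105.7.

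The plan states the 10% and 20% for Week 8 remitters; applying them to everyone remaining is an assumption. With f = 10%, about 8 esketamine-arm and 11 quetiapine-arm participants would supply all the events, while the percentages would be taken over about 80 and 106. These totals indicate scale only and do not enter the identity in Step 2.

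**The case against.** **The denominator is not written out.** It is inferred from the instruction on the analysis set plus the number-and-percentage format. SAP 5.10 also says that follow-up analyses present observed data only, and a programmer might take that as leave to drop participants with no adverse event collection. This does not settle the matter: elsewhere in the SAP observed data are contrasted with last observation carried forward, and the phrase sets no adverse event denominator.

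**The percentage is not arithmetically wrong.** This stands. The share of an arm's discontinuers who had an event on a Janssen product is a valid descriptive statistic. It misleads only when read as incidence, which is how adverse event tables are usually read. The treatment given during follow-up is also summarised under SAP 5.10, so a reader could partly rebuild the other denominator, though not re-sort events by product.

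**The table does not say that quetiapine caused the events.** This stands too. The row label names a Janssen treatment, the phase begins after study intervention stops, and the columns are declared as randomised groups. A reader might infer that the plan attributes esketamine events to the comparator; the documents do not go that far. Nor do they show that the events would mostly arise on commercial esketamine: other Janssen depression products qualify, availability varies by country and no counts are given.

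**No between-arm comparison is planned.** Correct: SAP 5.10 is descriptive. A reader could still compare the columns by eye.

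**Events are not confined to Janssen users throughout follow-up.** Also correct. Until the safety follow-up visit, about two weeks after the last dose, adverse events are collected from everyone and feed the treatment-emergent tables. The limit on collection begins after that visit; the limit on what this row counts applies throughout.

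**Conclusion.** The point holds for one descriptive table. As specified, the row shows a share of all discontinuers, equal to f times the incidence among those on a Janssen depression product. Its columns show randomised arm for events that arose on a treatment chosen later, and differences between them partly reflect switching rates. There is some dilution if any follow-up participant is not on a Janssen product, and some misplacement if any quetiapine-arm participant moves to one; the protocol permits both. The size cannot be fixed because f is not in the documents. The 5% to 20% range rests on an assumed f of 10% to 40% and an assumed true incidence of 50%.

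A reader might infer that the trial's safety comparison is compromised. The documents do not support that. The main treatment-emergent tables use the safety set by actual intervention received and close at the safety follow-up visit, with serious events to 30 days after the last dose. The primary and key secondary endpoints are untouched. The change is worth making because it is cheap and the table is easily misread.

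**What to change.** Amend SAP 5.10 for the adverse event row only:

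- Limit the denominator to follow-up participants who took a Janssen depression product during follow-up.
- Tabulate by product taken at event onset (commercial esketamine, other Janssen depression product), with randomised arm as a secondary breakdown. Give counts without percentages where numbers are small.
- Report time on the product, because discontinuation can occur at any point before Week 32 and exposure will vary.
- Add a footnote that adverse events on other standard of care were not systematically collected after the safety follow-up visit.

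The other SAP 5.10 parameters can keep the full set and randomised columns. The cost is a paragraph of SAP text and one extra table shell. No new data should be needed: concomitant therapy is recorded at the follow-up visits, and post-discontinuation treatment is already a SAP 5.10 parameter. The downside is small denominators, about 8 and 11 participants in the illustration with f = 10%, so the table would serve as description rather than a precise estimate of incidence.
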